The primary outcomes were established in the protocol, and thus no adjustments will be made for multiplicity.

14) Confidence intervals

95% confidence intervals will be reported alongside exact p-values.

15) Adherence and protocol deviations

- a. Definition of exposure to the intervention and how this is assessed including extent of exposure:
 - i. Receipt of medically tailored food support AND
 - ii. Receipt of nutrition counseling and/or education
- b. Description of how adherence to the intervention will be presented.

Adherence to the intervention will be presented through a narrative summarizing the following points:

- i. % of weeks received any food support (out of weeks scheduled to receive food support)
- ii. % of food received (out of total food entitlement) (POH data)
- iii. % of food consumed (out of food received) (survey data)

iv. % of counseling or education sessions received (out of planned sessions) The cut-off points to decide if the patient is adherent to the intervention will be defined during the analysis, based on the participant's exposure to the intervention.

Definition of protocol deviations for the trial. The following protocol deviation occurred during the study and corrective actions were developed:

- a. Minor protocol deviation: Participants for study visits were seen outside of the initial protocol specified visit window (+/- 1 month). All efforts were made to reach the participants on time, but the participants were not available or were not able to be located within the window and therefore they were seen outside of the visit window. As a result, the standard operating procedure (SOP) was updated that addresses follow up and retention of participants. The SOP outlines that the research assistants will make calls and conduct home visits in case a participant misses his or her appointment date to ensure that the participants are seen with the appointment window period.

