- 7. Emergency room utilization at any hospital from baseline to 1 month, as determined by ZSFGH medical records and self-report of emergency room utilization at hospitals other than ZSFGH. Number of admissions to any emergency room from baseline to 1 month, by study arm, adjusting for baseline values (-3 to 0 months).
- 8. Emergency room utilization at any hospital from baseline to 5 month, as determined by ZSFGH medical records and self-report of emergency room utilization at hospitals other than ZSFGH. Number of admissions to any emergency room from baseline to 5 months, by study arm, adjusting for baseline values (-3 to 0 months).

ii. Overall health-related quality of life. Self-reported quality of life using the 4-item Healthy Days Core Module of the CDC's Health-Related Quality of Life survey which asks a general assessment of health on a 5-point Likert scale as well as 3 questions quantifying the number of days in the past 30 days participants felt their health was not good.

c. Aim 2 Outcomes. The primary intermediate outcomes are changes between baseline, 1 month and 5 months in food security, diet quality, depressive symptoms, and medication adherence.

- i. Food Security: We measured food security status using the 10-item adult version of the USDA Household Food Security Survey Module (HFSSM) Access Scale (HFIAS). This scale has been validated in Spanish and English in the US and is the reference measure for food security in the US [citations]. The ten-item questionnaire covers domains of worry over, sufficiency of, and quality of food accessed by the participant's household. The scores will be analyzed primarily as a continuous variable using a sum of all responses with a possible range of 0 to 18 in households with children, and 0 to 10 in households without children. Higher scores are indicative of less food security. We will examine the following outcomes:
 - 1. Change in food security scores from baseline to 5 months, by study arm.
 - 2. Change in food security scores from baseline to 1 month, by study arm.

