- ii. Change in dietary patterns: Food consumption was collected using food frequency questionnaire that assess the frequency of intake of 32 food items in the prior month. A change in the consumption (servings/day) of food groups from baseline to one month, and from baseline to five months will be assessed. The food groups to evaluate are food high in: Unsaturated Fat (nuts), Saturated Fat, Sodium, Added sugars, Fruits, Vegetables (fresh), Vegetables (canned), Animal-based Protein, Plants-based Protein, Dairy, and Carbs/Starch.

- iii. Medication adherence. A Single-Item Rating Visual Analogue Scale (range 0-100) for medication adherence will estimate the percentage of medications taken in the past month and is reliable and valid, including in low-literacy populations. A higher value indicates higher adherence. The change in medication adherence (percentage points) from baseline to one month, and from baseline to five months between intervention and control arms will be reported.
- iv. Depressive symptoms. Symptoms corresponding to the Diagnostic and Statistical Manual of Mental Disorders will be measured using the 9-item Patient Health Questionnaire (PHQ-9), a reliable and valid measure of symptom severity. The PHQ-9 score ranges from 0 to 27, with higher scores indicating higher levels of depression. The change in PHQ-9 scores from baseline to one month, and from baseline to five months among by study arms will be reported.

d. Other outcomes.

- i. **Sustained health benefits:** To assess whether any improvements outcomes were sustained, researchers will evaluate the hospitalization and emergency department visits, four months after the intervention ended (at 9 months).

- 1. Admissions to Zuckerberg San Francisco General Hospital from baseline to 9 months, as determined by medical records. Number of admissions to Zuckerberg San Francisco General Hospital from baseline to 9 months, by study arm, adjusting for baseline values (-3 to 0 months).
- 2. Emergency room utilization at Zuckerberg San Francisco General Hospital from baseline to 9 months, as determined by medical records. Number of admissions to the emergency room at Zuckerberg San Francisco General Hospital from baseline to 9 months, by study arm, adjusting for baseline values (-3 to 0 months).

ii. Process outcomes 24)

23) **Analysis methods:**

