- a. **Preliminary/Descriptive analyses.** Frequency tables for all variables and measures of central tendency and variability for continuous variables will characterize the sample and be stratified by randomization arm to check for non-equivalence. If the two arms differ at baseline on any covariates, propensity scores approach will be used to obtain the desired marginal effect estimates under the counterfactual assumption of balanced arm.

25) Analysis methods to be used and how the treatment effects will be presented:

- a. Aim 1, Hypothesis 1. The intervention will lead to improved heart failure quality-of-life (primary outcome) and reduced acute care utilization (secondary outcomes) in the intervention arm compared to the control arm. Intent-to-treat analyses will assess whether the intervention will result in improved changes in primary and secondary outcomes with mixed effects models. These mixed models are equivalent to repeated measures models. Study arm (intervention or control), visits (baseline, month 1 and month 5), and the interactions between arms and visits will be the fixed effects and individuals will be considered as random effects.

Alternative analyses will be done using analysis of covariance in which the 5 month (and 1 month) outcome measures will be regressed on the corresponding baseline outcome measures and study arm. Analysis of covariance allows relaxing the assumption that the

baseline and follow-up measures have a 1:1 relationship and testing the assumption that the relationship between the baseline and follow-up measures are the same.

Additional analyses will be done to check robustness if the two arms differ at baseline by controlling for the propensity score or the covariates that were important in the propensity score.

For primary and secondary outcomes, Box-Cox transformations will be used to correct for skewness if needed.

To compare the probabilities of hospitalization and emergency room visits by study arm, a log-rank test will be performed, and visualized using Kaplan-Meier curves.

- b. Aim 2, Hypothesis, The intervention will improve food security, reduce healthcare utilization, and improve dietary behavior, that in turn will improve mental health (depressive symptoms), and medication adherence. Analysis for intermediate outcomes will be performed using mixed effects models, as described in Aim 1.
- c. Any planned sensitivity analyses for each outcome, where applicable: Not applicable.

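### Aim 2 calls its outcomes primary intermediate and sets out 28 unadjusted arm contrasts, 22 of them food groups, with no lead contrast and no exploratory label

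*Combined protocol and SAP*

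**What the plan says.** Section 6, item 22c, opens the Aim 2 outcomes with: "The primary intermediate outcomes are changes between baseline, 1 month and 5 months in food security, diet quality, depressive symptoms, and medication adherence".

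The four constructs are then specified as follows.

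- **Food security:** two contrasts, the first being "Change in food security scores from baseline to 5 months, by study arm"; the second is the same change to 1 month.
- **Diet (22c.ii):** no overall score. A 32-item frequency questionnaire is reduced to food groups, and "A change in the consumption (servings/day) of food groups from baseline to one month, and from baseline to five months will be assessed". These groups are "Unsaturated Fat (nuts), Saturated Fat, Sodium, Added sugars, Fruits, Vegetables (fresh), Vegetables (canned), Animal-based Protein, Plants-based Protein, Dairy, and Carbs/Starch".
- **Adherence to medication:** the arm difference in change, in percentage points, at each of the same two times.
- **PHQ-9:** change to one month and to five months, by arm.

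Item 25b (analysis methods, Aim 2) states a directional hypothesis: "The intervention will improve food security, reduce healthcare utilization, and improve dietary behavior, that in turn will improve mental health", and likewise medication adherence. It uses the same mixed models as Aim 1. Item 8 sets a superiority testing framework for the trial. Items 12 and 14 promise exact p-values with 95% confidence intervals. On multiplicity, item 13 says only: "The primary outcomes were established in the protocol, and thus no adjustments will be made for multiplicity".

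**The concern.** Aim 2 is the part of the trial that would explain how the food support works. The plan attaches the word primary to it and states what the intervention is expected to improve, but does not say which result would bear that out. No time point or food group leads, there is no composite diet score or testing order, and nothing in 22c or 25b is called exploratory.

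Item 13 does not fill the gap. If its reason is confined to the KCCQ outcomes, Aim 2 has no rationale at all. If it is meant to reach Aim 2, it does not help, because fixing a list of 28 contrasts in advance does not limit the chance that one of them is significant by luck.

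What is at stake is the wording of the Aim 2 conclusions, above all a claim of better diet. Diet holds 22 of the 28 chances, and 22c.ii gives no favourable direction for any food group. For groups such as dairy, animal protein or starch, a change either way could be presented as an improvement. The KCCQ comparisons of item 22a are a separate family and are not at issue here.

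**Working it through.** **1. The plan's own figure.** The documents give no error rate for Aim 2. The only stated alpha is in item 7, for the KCCQ: two-sided 0.05, 80% power, SD 20, difference 10. It reproduces: n = 2 × (1.960 + 0.842)² × 20²/10² = 62.8, so 63 per arm; 63/0.80 = 78.75, so 79 per arm and 158 in total. That calculation is sound and says nothing about Aim 2.

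**2. Number of contrasts (item 22c).**

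| Outcome | Measures | Times | Contrasts |
|---|---|---|---|
| Food security | 1 | 2 | 2 |
| Food groups | 11 | 2 | 22 |
| Medication adherence | 1 | 2 | 2 |
| PHQ-9 | 1 | 2 | 2 |
| Total | 14 | | 28 |

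This is a minimum, because 25b also puts healthcare utilization into the Aim 2 hypothesis.

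**3. Assumptions.** All null hypotheses are true. Each contrast is read at two-sided 0.05 (inferred from item 7 and the 95% intervals). Test statistics share one correlation r. The documents give no r, so 0.2, 0.5 and 0.8 are shown.

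**4. Formulas for k contrasts,** with Φ and φ the standard normal distribution and density:

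- Either direction: 1 − ∫ [Φ((1.96 − √r·u)/√(1−r)) − Φ((−1.96 − √r·u)/√(1−r))]^k φ(u) du.
- Favourable direction only: 1 − ∫ [Φ((1.96 − √r·u)/√(1−r))]^k φ(u) du. Each contrast then carries 0.025, with every statistic oriented so that positive means benefit.
- Independence (r = 0): 1 − 0.95^k and 1 − 0.975^k.

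**5. Results.**

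| Set | Direction | r = 0 | r = 0.2 | r = 0.5 | r = 0.8 |
|---|---|---|---|---|---|
| All 28 | either | 0.76 | 0.70 | 0.49 | 0.25 |
| All 28 | favourable | 0.51 | 0.39 | 0.25 | 0.13 |
| 22 diet | either | 0.68 | 0.62 | 0.44 | 0.23 |
| 22 diet | favourable | 0.43 | 0.34 | 0.22 | 0.12 |
| 6 non-diet | either | 0.26 | 0.25 | 0.21 | 0.14 |
| 6 non-diet | favourable | 0.14 | 0.13 | 0.10 | 0.07 |

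The expected number of false positives does not depend on r: 28 × 0.05 = 1.4 in either direction, 28 × 0.025 = 0.7 favourable.

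**6. Check on the correlation structure.** A simulation (200,000 draws) kept the two time points and the 14 outcomes distinct. With correlation 0.5 between times and 0.1 to 0.3 between outcomes, the rates were 0.72 to 0.66 in either direction and 0.44 to 0.36 favourable. Over the whole grid (times 0 to 0.7, outcomes 0 to 0.5) they ran from 0.76 to 0.51 and from 0.51 to 0.26. The size depends on the assumed structure, but no setting comes near the nominal 0.05 or 0.025.

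**The case against.** A reader might infer that a false improvement is about as likely as not. The documents do not support that as a general statement. The 0.49 at r = 0.5 counts false worsening as well as false improvement. In one prespecified direction the figure at the same r is 0.25, and it reaches 0.51 only if all 28 contrasts are independent, which is implausible for repeated visits and for food groups from one questionnaire. The missing direction for food groups pushes the true exposure above the favourable-only figures, by an amount the documents do not determine.

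A reader might also infer that the plan lets any one of the 28 contrasts carry the claim. It contains no such rule. Items 12 and 14 set no threshold, and 25b frames the hypothesis by domain. Pooling all 28 into one family is a reviewer's choice. What stands is that nothing in the plan excludes that use.

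The strongest defence is rank. Aim 1 names heart failure quality of life as primary and utilization as secondary, Aim 2 outcomes are described as possible steps on the causal path, and item 5 calls the trial a pilot. Primary intermediate may simply mean the main mediators, and leaving mediators in a pilot unadjusted is defensible. So it would be wrong to say the plan has no hierarchy; the gap is within Aim 2. But item 5 ties its preliminary wording to quality of life, readmission and emergency visits, and no Aim 2 result is made conditional on Aim 1. Neither point serves as an exploratory label.

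Finally, a formal correction across mediators would be more than this SAP applies to its primary outcome. That is fair, and it is why correction is optional below.

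**Conclusion.** The point holds as a gap in labelling and interpretation within Aim 2. The count of 28 (22 of them diet) and the absence of a lead contrast or exploratory label rest on the text alone. The error rates rest on three assumptions: no true effects, reading at two-sided 0.05, and a correlation the documents do not give. On those, the chance of at least one significant result is 0.49 in either direction (0.70 to 0.25) and 0.25 for a false improvement in one prespecified direction (0.39 to 0.13). Diet alone accounts for 0.44 and 0.22 at r = 0.5; the six other contrasts give 0.21 and 0.10. The primary KCCQ conclusion is untouched. The change should be made, because the Aim 2 claims, diet first, are otherwise open to chance findings.

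**What to change.** **Item 22c.** Drop the word primary from the Aim 2 label. Make month 5 the lead time point for food security, medication adherence and PHQ-9. Label all month-1 contrasts and all food-group contrasts exploratory, reported as estimates with 95% confidence intervals and without significance claims. If the sponsor wants diet to have a lead contrast, choose one diet measure, with its favourable direction, and record it before the arm comparison is run. Item 10 puts the end of field data collection in Fall 2020 and the start of analysis in Fall 2021, so the choice counts as made in advance only if it precedes that analysis.

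**Item 13.** State that Aim 2 results are unadjusted and support no confirmatory claim.

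**Optional.** If confirmatory Aim 2 claims are wanted, apply Holm to one month-5 contrast per domain. With four domains the smallest p-value must reach 0.05/4 = 0.0125.

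**Cost.** SAP wording only, no new data. Of the 28 contrasts, 22 food-group and 3 other month-1 contrasts (25 in all, or 24 if one diet measure is chosen) can no longer support a stand-alone claim of improvement.

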We conducted a pilot randomized controlled trial (RCT) of an intervention providing five months of medically tailored meals (tapering down the amount of food each month), paired with nutrition education, to patients upon discharge from a safety-net hospital due to congestive heart failure (CHF) exacerbation. Participants were randomized to the intervention (n=106) versus control (n=86) using a parallel design. The goal was to test for feasibility and determine the preliminary impact of the intervention on heart-failure quality-of-life (primary outcome), and on in hospital readmission and emergency department visits (secondary outcomes). We also set out to determine the impact of this intervention on intermediate outcomes important to the health of our population (food security, diet, mental health and medication adherence), which may be on the path from the intervention towards improved heart failure health outcomes. The control arm continued with usual care during the study period and then received the five-month meal program starting the sixth month after discharge from the hospital. Participants were followed with full surveys at baseline, 1 month and 5 months; brief versions of the survey were administered at 2- and 3-months. In addition, we collected medical record data on healthcare utilization outcomes. Alongside the trial, a qualitative study and process evaluation was conducted, which included in-depth interviews with study participants and survey items added to the end-line survey to translate lessons learned to guide a possible scale-up of the intervention.

6) Randomization

Initially, 148 participants were randomized in a 1:1 allocation to the intervention (n=75) and control arms (n=73), stratified by food security (zero affirmative answers vs. at least one affirmative answers on the USDA 12-question food security screener) and healthcare utilization (<3 vs. >=3 hospital admissions at ZSFGH), based on a computer-generated assignment. However, early withdrawals were observed, which was higher in the intervention (n=27) than in the control arm (n=3). Therefore, the randomization of the last 44 participants were allocated in a 2:1 ratio for intervention (n=31) relative to control (n=13) arms to compensate for early withdrawals and have the final study arms balanced.

7) Sample size

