Estimates from the literature were used to calculate the sample size needed for this study for the outcomes of changes from month 0 to month 5 in our primary outcome, heart failure quality-of-life. We assumed that the standard deviations (SD) seen in the current study would be similar to that in a similar study conducted in an urban setting in the United States.¹³ Sample size calculation were based assuming 80% power for a two-sided test at alpha of 0.05, and SD of 20.0. With the outcome of change in heart failure quality of life score from baseline to 5 months, considering as a minimum clinical difference of 10 points in the heart failure quality of life score, the sample size

needed was 63 individuals in each arm. We assumed a retention in the current study of 80%, thus the sample size needed at recruitment was at least 158 (n=79 in each arm)

8) Framework

The superiority hypothesis testing framework will be used, testing whether exposure to the intervention results in better outcomes than exposure to the control standard of care. Comparisons will be presented as differences between arms in changes in outcomes from baseline to 1 month to capture changes in acute heart failure symptoms and 30-day readmission; and from baseline to 5 months of follow-up to capture longer term and potentially sustained benefits.

9) Statistical interim analyses and stopping guidance

- a. Information in interim analyses specifying what interim analyses will be carried out and listing time points
 - i. None planned
- b. Any planned adjustment of the significance level due to interim analysis
 - i. No
- c. Details of guidelines for stopping the trial early
 - i. None

10) Timing of final analyses

Final analyses will begin in Fall 2021 upon completion of all field data collection in Fall 2020 and completion of all medical record data collection (Summer 2021).

11) Timing of outcome assessments

Research staff administered full surveys to both arms at baseline, 1 month, and 5 months. Additional brief surveys were collected at months 2 and 3. Medical record data were collected continuously in both arms from 3 months prior to baseline until 9 months after baseline.

Section 4: Statistical Principles

12) Level of statistical significance

95% confidence intervals and exact p-values (or $p<0.001$) will be reported.

13) Description and rationale for any adjustment for multiplicity and, if so, detailing how the type I error is to be controlled.

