- b. Unable to be contacted: 16 intervention participants were randomized but were not able to be contacted by POH to start the intervention and were considered as early withdrawals. Control participants could not be excluded as "early withdrawals" because the next visit would be a month after the baseline. Therefore, researchers modified the protocol and made a phone call to the control participants, right after the randomization, to simulate the call that the intervention participants had by POH to be enrolled in the food and nutrition program. From among control participants called right after randomization in the modified protocol, 2 could not be reached and were considered early withdrawals.

The number of participants with major and minor protocol deviations will be summarized by study arm.

16) Analysis populations – definition of analysis populations, e.g. intention to treat, per protocol, complete case, safety

- a. Intent to treat - The primary analysis will be intent to treat (ITT). The ITT analysis will include all participants in both arms who were randomized, completed all baseline assessments, and who had at least one follow-up visit. (see CONSORT).
- b. Adjusted intention to treat analysis. To adjust for early withdrawals, a propensity score for receiving the intervention will be developed and used to estimate the probability of each participant to receive the intervention. The adjusted ITT analysis will be performed adjusting for the propensity score and for baseline covariates that were different between arms.
- c. Per protocol - The per protocol analysis will include all participants in the ITT sample with baseline and follow-up evaluations and who adhered to the food and nutrition intervention. The minimal adherence will be considered as receiving at least 50% of weeks food and groceries, and at least 1 visit with the dietitian. This definition may be

revised depending on the distribution of adherence in the intervention participants. See appendix 1 for details about the food and nutrition education intervention.

- d. Complete case— We will not conduct complete case analyses as we will attempt to use all available data from all participants.

Section 5: Trial Population

17) Screening Data –

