 1. 16 (15.1%) of randomized intervention and 2 (2.3%) of randomized control participants were unable to be contacted by phone after the baseline evaluations.
 2. 6 (5.7%) participants allocated to the intervention and 2 (2.3%) participants allocated to the control arm were excluded because did not meet eligibility criteria after randomization, and 3 (2.8%) participants in the intervention arm were immediately re-hospitalized.
 3. 1 (0.9%) participant in the intervention arm died after being randomized.
 - ii. Lost to follow up (LTFU) occurred through loss of contact with study participants, moving out of the study area, and death. Intervention participants were also considered LTFU if they withdrew consent. Among

those that were randomized and contacted immediately after randomization (n=79 in intervention arm, and n=82 in control arm):

1. At month 1, 75 (94.9%) of intervention participants and 78 (95.1%) of control participants were retained from month 0.
2. At 5 months of follow-up, 60 (75.9%) of intervention participants and 59 (71.9%) of control participants were retained from month 0.

b. Timing of withdrawal/LTFU data

- i. Intervention participants left the study prior to their first encounter with Project Open Hand were considered withdrawn, otherwise they were considered LTFU.
- ii. Control participants that left the study prior the first call from UCSF staff were considered withdrawn, otherwise they were considered LTFU.
- iii. Participants that were excluded immediately after randomization were also considered early withdrawals.

c. Reasons and details of how withdrawal/LTFU data will be presented

- i. Withdrawal and LTFU data are presented in the CONSORT diagram, stratified by study arm and visit. These data are included to establish lack of bias in screening and retention between the two arms. (See appendix 2)

21) Baseline patient characteristics

We will evaluate several socio-demographic and clinical characteristics at baseline by which we will describe our study sample. These are outlined in Table 1 below and a shell table is provided in the appendix. We will stratify these characteristics by intervention and control arms and report median and the inter-quartile range for continuous variables with skewed data and mean and SD for continuous variables with normal distribution. Categorical variables will be presented as numbers and percentages. No significance testing will be conducted or reported at baseline per CONSORT guidelines.

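### The KCCQ models omit both stratification factors and the allocation phase, while further covariates are chosen by an undefined baseline difference that is likely to arise by chance

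*Combined protocol and SAP*

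**What the plan says.** **Allocation (Section 3, item 6).** Randomisation was "stratified by food security (zero affirmative answers vs. at least one affirmative answers" and by fewer than three versus three or more hospital admissions. The first 148 participants were allocated 1:1 (75 intervention, 73 control). The last 44 were allocated 2:1 (31 and 13), to compensate for early withdrawals.

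**Models (Section 6, the item numbered 25 on analysis methods, part a).** The primary mixed model has arm, visit (baseline, month 1, month 5) and their interaction as fixed effects, with a random effect for the individual. The alternative ANCOVA regresses the follow-up score on the baseline score and arm. Food insecurity returns only as a possible subgroup interaction.

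**Further covariates.** Three places make the choice depend on what is observed at baseline:
- Item 23a: "If the two arms differ at baseline on any covariates, propensity scores approach will be used".
- Item 25a: robustness analyses, again conditional on a baseline difference, using either the propensity score or the covariates that mattered in it.
- Section 4, item 16b: an adjusted ITT analysis "adjusting for the propensity score and for baseline covariates that were different between arms".

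No threshold for a difference and no covariate list is given. Item 21 adds: "No significance testing will be conducted or reported at baseline per CONSORT guidelines".

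**The concern.** There are two separate weaknesses.

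First, the models do not reflect how participants were allocated. Stratification makes the arms alike on the strata. If the strata predict the analysed outcome, a model without them overstates the standard error and gives away precision. Allocation phase is different. The change of ratio makes the arms unlike in when participants were enrolled, so a difference in outcome between early and late enrolees passes into the treatment contrast as bias. Conditions may have differed: Appendix 1 mentions COVID-19 changes to dietitian visits and item 10 puts the end of field collection in Fall 2020. The plan does not date the switch, however.

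Second, choosing covariates by observed imbalance ignores whether they predict the outcome, and leaves the adjusted analyses to the analyst's judgement after looking at the data. Item 21 rules out the one conventional criterion, rightly, but nothing replaces it.

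**Working it through.** **1. The plan's own figure.** Section 3, item 7 gives "assuming 80% power for a two-sided test at alpha of 0.05, and SD of 20.0" and "considering as a minimum clinical difference of 10 points in the heart failure quality of life score". Then n per arm = 2 × (1.96 + 0.84)² × 20² / 10² = 62.7, rounded up to 63, which agrees with "needed was 63 individuals in each arm". With 80% retention, 63 / 0.80 = 78.75, so 79 per arm and 158 in all. The sample size reproduces. Item 20 reports 60 and 59 retained at month 5, slightly below 63; power at the planned SD is then about 0.78.

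**2. How often the trigger fires by chance.** Table 1 lists 6 + 3 + 4 + 2 + 1 + 3 + 3 = 22 characteristics (my count). The plan sets no criterion, so each one below is an assumption.
- 5% level, independent: 1 − 0.95^22 = 0.68.
- 5% level, equal correlation of 0.2 or 0.4 (simulated, 200,000 draws): 0.62 or 0.51.
- Standardised difference above 0.2 with 79 and 82 participants: the standard error is √(1/79 + 1/82) = 0.158, so the chance is 0.20 per characteristic, and 1 − (1 − 0.2046)^22 = 0.99 for any of 22 if independent.

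**3. Omitting the strata.** Let R² be the share of variance of the analysed outcome that the strata explain. The documents give no value. With strata balanced between arms, the unadjusted test statistic has variance 1 − R², so true alpha = 2 × [1 − Φ(1.96 / √(1 − R²))]. For power at 63 per arm, c = 10 / (20 × √(2/63)) = 2.81. Power is 1 − Φ((1.96 − c) / √(1 − R²)) without the factors and Φ(c / √(1 − R²) − 1.96) with them.

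| Assumed R² | True alpha, omitted | Power, omitted | Power, included | n per arm, included |
|---|---|---|---|---|
| 0 | 0.050 | 0.801 | 0.801 | 63 |
| 0.05 | 0.044 | 0.807 | 0.821 | 60 |
| 0.10 | 0.039 | 0.814 | 0.841 | 57 |
| 0.20 | 0.028 | 0.828 | 0.881 | 51 |

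Simulated stratified allocation (161 participants, 20,000 repeats) gave alpha of 0.038 at R² 0.10 and 0.028 at R² 0.20 with the factors omitted, and about 0.05 with them included.

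**4. What R² means in the mixed model.** Baseline is one of the response visits, and the effect of interest is arm by visit, a contrast in change. A factor that moves a participant's score equally at all visits cancels from that contrast. The table therefore applies to the mixed model only if the strata predict change and enter with visit interactions. In the ANCOVA it applies to variance left after the baseline score.

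**5. Omitting phase.** Late enrolees are 31/106 = 29.2% of the intervention arm and 13/86 = 15.1% of control, a gap of 14.1 percentage points. If mean change differs between phases by d points, the unadjusted contrast shifts by 0.141 × d:
- d = 5 (assumed): 0.7 points.
- d = 10 (assumed): 1.4 points.

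These are shares of those randomised. The ITT set in item 16a excludes participants without follow-up. If the 27 and 3 early withdrawals cited in item 6 all came from the first 148, the sets after withdrawal would be 48 + 31 = 79 and 70 + 12 = 82. The gap would then be 31/79 − 12/82 = 39.2% − 14.6% = 24.6 points, and the shift 1.2 to 2.5 points. The documents do not settle this, so I take the smaller range as the size.

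**The case against.** The strongest reply is that little of this touches the primary estimate. Item 16a makes the ITT analysis primary, and item 25a calls its conditional adjustment a robustness check; only item 23a is unclear about which analysis it governs. This stands. A reader might infer that the analyst's eye decides the primary result, but the documents do not show that.

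Nor do covariates enter only through the trigger. The ANCOVA always includes the baseline outcome, the utilisation outcomes always adjust for the three months before baseline, and item 16b plans a propensity score unconditionally, though its covariates are unnamed.

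Item 16b also has a stated purpose: early withdrawals, which were 27 of 106 against 4 of 86 (25.5% and 4.7%). Imbalance in the analysed set may therefore reflect selection and not chance, so the figures for sound randomisation are a benchmark, not a description of this trial. That also stands, and it is a reason to keep item 16b. It does not rescue the covariate rule, since a fixed list serves differential withdrawal better than an undefined difference.

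A reader might further infer that leaving out the strata inflates type I error, or that adding them must shrink the variance. Neither follows. With balanced strata the omission is conservative, and the gain is zero if they do not predict the analysed outcome.

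Finally, the trial calls itself a pilot. That lowers the stakes, but the plan still tests for superiority on KCCQ.

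**Conclusion.** The concern holds in this form: the allocation factors are missing from both KCCQ models, and the further covariates have no usable selection rule.

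- **Strata:** a loss of efficiency, not a false-positive risk. True alpha is 0.044 to 0.028 at an assumed R² of 0.05 to 0.20. This assumes that the strata are balanced in the analysed set, which uneven withdrawal may disturb.
- **Phase:** a possible bias of about 0.7 to 1.4 KCCQ points, or 7% to 14% of the 10-point difference planned for. It rests on an assumed 5 to 10 point difference in change between phases, and is nil if there is none.
- **Trigger:** more likely than not to fire by chance under each criterion tried (51% to 68% at the 5% level). It affects the adjusted analyses, and the primary one only if item 23a is read that way.

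This should be changed, but it does not invalidate the trial.

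**What to change.** 1. Add both stratification factors and allocation phase (1:1 or 2:1) to the mixed model, each with its interaction with visit. Main effects alone would leave the change contrast almost untouched. Do not add baseline KCCQ as a covariate there, since it is already a response.
2. Add the same three factors to the ANCOVA as main effects.
3. In items 23a and 25a, replace the condition on baseline difference with a fixed list of prognostic covariates, set before outcomes are examined. In item 16b, use that list in place of covariates found to differ.
4. Keep the item 16b propensity-score analysis, built from that list, as a prespecified sensitivity analysis for differential early withdrawal.
5. State in item 23a that it does not alter the primary analysis.

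The cost is SAP wording and a few degrees of freedom: three terms in the ANCOVA, and nine in the mixed model (three factors, each with one main effect and two visit interactions).
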